#### **4.5. Safety Endpoints**

- Safety and tolerability of SEL-212 as assessed by adverse events (AEs), AEs of special interest (AESIs), serious AEs (SAEs), deaths, and discontinuations due to AEs
- Additional safety assessments will include review and evaluation of laboratory testing including hematology, coagulation, chemistry, urinalysis; vital signs; immunogenicity analyses; 12-lead ECGs; and physical examination findings.

This document is confidential.

## **5. Analysis Sets**

### **5.1. Screened / Randomized Set**

The Screened Set will include all patients who signed an informed consent. The Randomized Set will include all patients who were randomized. The Randomized Set will be used for the presentation of patients in all patient listings. Randomized but not treated subjects will be replaced.

### **5.2. Safety Set**

The Safety Set (SS) will include all patients who were administered any amount of study medication. Patients will be analyzed according to treatment received.

### **5.3. Intent-to-Treat Set**

The Intent-to-Treat (ITT) Set will include all randomized patients who were dosed. Patients will be analyzed according to randomized treatment group assignment. Replaced subjects will not be included in the ITT. The ITT will be used as primary population for analyses of efficacy endpoints.

### **5.4. Modified Intent-to-Treat**

A modified ITT (mITT) population will be defined as a result of the COVID-19 pandemic. The COVID-19 pandemic could potentially impact the ability to attend visits and/or receive treatment.

The modified ITT (mITT) will include all randomized patients who were dosed, except those who discontinue treatment due to a COVID-19 infection as defined in the study protocol or do not have at least 2 sUA measurements 7 days apart in TP6 due to a/multiple missed visits due to a COVID-19 infection or subsequent complications as defined in the study protocol.

Patients will be analyzed according to randomized treatment.

### **5.5. Per Protocol Set**

The Per Protocol Set (PPS) will include all patients who were administered at least one complete dose of study medication, who have at least one post-baseline assessment of sUA, who have sufficient data to assess the primary efficacy endpoint, and who have no major Protocol deviations affecting the primary efficacy assessments. Patients will be analyzed according to randomized treatment. PPS will be defined for the double-blind treatment phase of the study, only.

### **5.6. All randomized Set**

The all randomized set will include all patients who were randomized. Patients will be analyzed according to randomized treatment group assignment.

### **5.7. Extension Phase Evaluable Set**

The Extension Phase Evaluable Set (EPS) will include all patients of the safety set who continue into the double-blind extension phase.

This document is confidential.

## **5.8. Protocol Deviations**

All protocol deviations related to study inclusion or exclusion criteria, conduct of the trial, patient management, dosing, and sampling procedures or patient assessment will be listed. The list of protocol deviations will be reviewed by the Sponsor, the principal investigator and the study statistician and finalized before database lock. Determination of whether the deviation is major or minor, or has impacts on primary efficacy assessment will be based on the biasing impact of the deviation on the safety and efficacy data.

The use of the following medications/therapies during the trial is not allowed and will be considered as major protocol deviations impacting the primary efficacy assessments:

- Uric acid lowering therapy (ULT) including, but not limited to allopurinol, febuxostat (Uloric®), probenecid, lesinurad (Zurampic®, Duzallo®), losartan, pegloticase (Krystexxa®) and benzbromarone ULT. Patients on a stable long term dose of losartan may be allowed to continue in the study without changing to another angiotensin II receptor blocker.
- The use of CYP3A4 moderate and severe inducers or inhibitors are prohibited 14 days prior to dosing and during the trial.

Protocol deviations will be assessed for the double-blind treatment phase and the double-blind extension phase. Protocol deviations will be summarized separately for the double-blind treatment phase and for the double-blind extension phase.

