8.2 Patient Exclusion Criteria

A patient who meets any of the following criteria will be excluded from this study:

1. Has a history of anaphylaxis, severe allergic reactions, or severe atopy;
2. Has a history of any allergy to pegylated products, including, but not limited to pegloticase (Krystexxa®), peginterferon alfa-2a (Pegasys®), peginterferon alfa-2b (PegIntron®), pegfilgrastim (Neulasta®), pegaptanib (Macugen®), pegaspargase (Oncaspar®), pegademase (Adagen®), peg-epoetin beta (Mircera®), pegvisomant (Somavert®) certolizumab pegol (Cimzia®), naloxegol (Movantik®), peginesatide (Omontys®), and doxorubicin liposome (Doxil®);
3. Is taking and cannot discontinue known major CYP3A4/P-gp inhibitors or major CYP3A4/P-gp inducers at least 14 days before dosing. Patients must remain off these medications for the duration of the study, including natural products such as St. John's Wort or grapefruit juice.

4. Is taking drugs known to interact with rapamycin (sirolimus – Rapamune[®]) such as cyclosporine, diltiazem, erythromycin, ketoconazole, posaconazole, voriconazole, itraconazole, rifampin, verapamil unless they are stopped 14 days prior to dosing and will not be used/prescribed during the trial.
5. Had major surgery within 3 months of initial screening.
6. Had a gout flare during Screening that was resolved for less than 1 week prior to first treatment with study drug (exclusive of chronic synovitis/arthrits) unless the patient has a history of inter-flare intervals of < 1 week.
7. Has uncontrolled diabetes at Screening with HbA1c ≥ 8.5%;
8. Has fasting Screening glucose > 240 mg/dL
9. Has fasting Screening triglyceride > 500 mg/dL;
10. Has fasting Screening low-density lipoprotein (LDL) > 200 mg/dL;
11. Has glucose-6-phosphate dehydrogenase (G6PD) deficiency;
12. Has uncontrolled hypertension defined as blood pressure > 170/100 mmHg at Screening and 1 week prior to dosing
13. Individual laboratory values which are exclusionary
 - White blood cell count (WBC) < 3.0 x10⁹/L
 - Serum aspartate aminotransferase (AST) or alanine amino transferase (ALT) > 3x upper limit of normal (ULN) in the absence of known active liver disease
 - Estimated Glomerular filtration rate (eGFR) < 30 mL/min/1.73 m²
 - Urine-albumin-creatinine ratio (UACR) > 30 mg/g creatinine (conventional units) or > 3.39 mg/mmol creatinine (SI units)
 - Hemoglobin (Hgb) < 9 g/dL
 - Serum phosphate < 2.0 mg/dL

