9.2.2 CYP3A4/P-gp Inducers and Inhibitors

The use of CYP3A4/P-gp major inducers or major inhibitors are prohibited 14 days prior to dosing and during the trial. Examples of major inducers include, but are not limited to carbamazepine-Tegretol®, phenobarbital, phenytoin-Dilantin®, rifampin/rifampicin-Rifadis®, St. John's Wort-Hypericum perforatum. Examples of major inhibitors include, but are not limited to nefazodone-Serazone®, itraconazole-Sporanox®, ketoconazole-Nizoral®, voriconazole-Vfend®, atraznavir-Reyataz®, indinavir-Crixvan®, nelfinavir-Viracept®, ritonavir-Norvir, saquinavir-Invirase®, clarithromycin-Biaxin®, telithromycin-Ketek®, and grapefruit juice.

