9.2.3 Other Concomitant Medications

Patients on medications (e.g., antifungals and/or calcium channel blockers) that do not rely on a mechanism of action that is known to increase the level or effect of rapamycin (sirolimus – Rapamune®) are permitted to continue taking these medications prior to and during the study, and will not be noted as a protocol deviation.

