13. STATISTICS

Details of the statistical methods outlined in the protocol for this study, including the hierarchical ordering of the secondary endpoints, will be documented in a Statistical Analysis Plan (SAP), which will be finalized prior to database lock. The SAP may add additional exploratory analyses; modifications to the planned analyses will be identified as such in the final SAP.

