## **12. Deviation from Analyses Planned in Protocol**

The key secondary endpoints for gout flare will be analyzed by ANOVA instead of ANCOVA as specified in the protocol, as adjustment for baseline is not possible given gout flare incidence is not assessed at baseline.

This document is confidential.

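### SAP 5.8 calls moderate CYP3A4 agents prohibited where the protocol bars only major ones, so supportive analyses could treat a protocol-compliant patient as a major deviator

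*SAP*

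**What the plan says.** SAP 5.8 (Protocol Deviations) lists medicines that are not allowed during the trial. Its second bullet reads: "The use of CYP3A4 moderate and severe inducers or inhibitors are prohibited 14 days prior to dosing and during the trial". The lead-in to the list says that use of a listed medicine "will be considered as major protocol deviations impacting the primary efficacy assessments".

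Protocol 9.2.2 has almost the same sentence with a different threshold: "The use of CYP3A4/P-gp major inducers or major inhibitors are prohibited 14 days prior to dosing and during the trial". Protocol 8.2, exclusion 3, uses that threshold too: "Is taking and cannot discontinue known major CYP3A4/P-gp inhibitors or major CYP3A4/P-gp inducers at least 14 days before dosing". SAP 3.4.2, exclusion 3, repeats the protocol's text.

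Two further protocol provisions matter:

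- Exclusion 4 separately excludes a patient who meets this description: "Is taking drugs known to interact with rapamycin". Its examples are open-ended and include cyclosporine, diltiazem, erythromycin, verapamil and rifampin. Such drugs must be stopped 14 days before dosing and not used during the trial.
- Section 9.2.3 covers medicines (antifungals and calcium channel blockers are its examples) that do not act through a mechanism known to raise the level or effect of rapamycin. Patients on them "are permitted to continue taking these medications prior to and during the study, and will not be noted as a protocol deviation".

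**The concern.** The two documents give different answers to what is prohibited, and the SAP also disagrees with itself. This matters because SAP 5.8 feeds two definitions used in the efficacy analyses. A major deviation affecting the primary assessment removes a patient from the Per Protocol Set (SAP 5.5). Use of a prohibited medicine that does not lower sUA, where classed as a major deviation, is a listed intercurrent event (SAP 6.1).

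A patient could therefore follow the protocol, meet the sUA criterion, and still be dropped or counted as a failure in some supportive analyses for taking a medicine that the protocol allowed. Those finalizing the deviation list before database lock would have two conflicting rules to choose between.

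**Working it through.** The plan gives no figure on this point, so the check compares texts, follows the rule through the analyses, and adds simple arithmetic.

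**1. The rules side by side**

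| Source | Agents barred |
|---|---|
| SAP 5.8 | CYP3A4, moderate and severe; P-gp not mentioned; exclusion 4 drugs not mentioned |
| Protocol 9.2.2 | CYP3A4/P-gp, major |
| Protocol 8.2, exclusion 3 | CYP3A4/P-gp, major |
| SAP 3.4.2, exclusion 3 | CYP3A4/P-gp, major |
| Protocol 8.2, exclusion 4 | Drugs known to interact with rapamycin (open list) |
| SAP 3.4.2, exclusion 4 | As above, but extended to other antifungals and other calcium channel blockers as classes |

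SAP 5.8 is the only place where the CYP3A4 rule reaches moderate agents. The last row is a second mismatch: the protocol's exclusion 4 has no such class-wide wording, and protocol 9.2.3 expressly allows some antifungals and calcium channel blockers.

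**2. Who could be affected.** Only a patient who takes an agent that counts as moderate, is not major, and is not already barred by protocol exclusion 4. The documents name no such agent. *Major* is illustrated by examples but not defined, and *moderate* and *severe* are not defined at all.

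**3. Effect on each analysis for such a patient,** assuming the agent does not itself lower sUA:

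- Main primary estimand, ITT: treatment policy applies, so no change.
- Second and fourth primary estimands, ITT: treatment policy also applies to this event, so no change.
- Third primary estimand: the composite strategy applies to every listed event, so the patient is a failure.
- Second estimands of the key secondary endpoints in SAP 6.2.1–6.2.4 and 6.2.6–6.2.9: while-on-treatment handling applies to all events listed in 6.1, so it is triggered. The endpoint in 6.2.5 follows the second primary estimand and is not affected this way.
- Any analysis on the Per Protocol Set: the patient is removed.

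**4. Reach, counted as estimand-by-population analyses:**

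- Per Protocol Set: 3 primary estimands (main, second, third) + 9 key secondary endpoints × 2 estimands = 21.
- Third primary estimand on ITT, mITT and all randomized: 3.
- Second estimands of eight key secondary endpoints on the same three sets: 8 × 3 = 24.
- Total: up to 21 + 3 + 24 = 48, each with two comparisons against placebo. Subgroup repeats are not counted.

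*Up to* is needed because the SAP does not say how while-on-treatment handling would cut the data of a patient who takes such an agent but stays on study drug.

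**5. Size per patient at the planned 40 per arm.** One reclassified responder changes the third-estimand ITT rate in that arm by 1/40 = 2.5 percentage points. From the planning rate of 45% (18/40) in an active arm, one reclassified responder gives 17/40 = 42.5%, two give 16/40 = 40.0%, and three give 15/40 = 37.5%. A reclassified non-responder changes nothing there. In the Per Protocol Set the patient is lost either way, so an arm of 40 becomes 39. No rate of use is assumed.

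**The case against.** The strongest reply is that the affected group may be empty. Exclusion 4 is open-ended, applies during the trial, and names drugs such as diltiazem, erythromycin and verapamil that are not among the examples in protocol 9.2.2. It also names an inducer, rifampin. Many moderate agents may therefore be barred already, and 9.2.3 does not clear a drug known to raise rapamycin levels. This stands: the documents do not show that any patient would be misclassified, only that the rule allows it.

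A reader might also infer an undeclared change to the planned analyses. Protocol Section 13 promises that "modifications to the planned analyses will be identified as such in the final SAP", and the only departure in SAP Section 12 is this: "The key secondary endpoints for gout flare will be analyzed by ANOVA instead of ANCOVA as specified in the protocol". The documents do not support making that the main charge. Protocol 13.2.5 leaves Per Protocol exclusion criteria to the SAP, and 13.4.1 and 13.4.2 leave further estimands to it. The protocol has no third primary estimand from which the SAP could depart. That freedom does not, however, extend to describing a medicine as prohibited in the trial when the protocol does not prohibit it.

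Finally, SAP 5.8 says that deviations are graded by their biasing impact, so reviewers might overrule the bullet. But the lead-in to the list fixes the classification, and the text does not clearly let reviewers set it aside.

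**Conclusion.** The contradiction is real and minor. SAP 5.8 misstates what the trial prohibits: it is wider than the protocol on CYP3A4 potency, and narrower in omitting P-gp and the exclusion 4 drugs. Followed as written, it could change Per Protocol membership and intercurrent-event status for a compliant patient.

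The effect depends on at least one patient using a moderate agent outside exclusion 4, and that number is unknown and may be zero. The 2.5 points per responder is the weight of one patient in 40, not a forecast of impact. The conclusion also assumes that the deviation list is built from SAP 5.8 as worded.

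A reader might infer a threat to the primary result. There is none: the main estimand keeps the observed sUA data after this event, and SAP 9.2 makes only the main estimand confirmatory.

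**What to change.** Replace the CYP3A4 bullet in SAP 5.8 with the protocol's rule: major CYP3A4/P-gp inducers or inhibitors as in 9.2.2, plus the rapamycin-interacting drugs of protocol exclusion 4, with the allowance in 9.2.3. Align SAP 3.4.2, exclusion 4, with the protocol's wording; otherwise the second mismatch remains.

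If a stricter rule is wanted for the Per Protocol Set, state it as an exclusion criterion for that set only. Do not describe the medicines as prohibited, and keep them out of the intercurrent-event definition in SAP 6.1.

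The cost is two text edits before database lock. No new data are needed and the confirmatory test is not touched.

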## **5.9. Subgroup analyses**

For analyses examining number of tender joints (see 6.2.6) and gout flare incidence (see 6.2.8), an additional subgroup analysis will be performed, stratifying by background medication taken in the seven days prior to Day 0 of Treatment Period 1 with intention to continue for as long as the patient is participating in the clinical study. Three strata will be defined: i) those who took neither non-steroidal anti-inflammatory drugs (NSAIDs) or colchicine at any point over the seven days prior to Day 0 of Treatment Period 1, ii) those who took NSAIDs and not colchicine at any point over the seven days prior to Day 0 of Treatment Period 1, and iii) those who took colchicine at any point over the seven days prior to Day 0 of Treatment Period 1. Participants who took both NSAIDs and colchicine in the seven days prior to Day 0 of Treatment Period 1 will be classified into strata iii).

For the primary analysis results will be presented stratified by age ( $\leq 50$  years old /  $> 50$  years old), race (white / non-white).

This document is confidential.

## **6. Estimands for Primary and Key Secondary Efficacy Endpoints**

### **6.1. Estimands are defined for the confirmatory analysis of efficacy in the double-blind treatment period. Estimands for Primary Efficacy**

The **main estimand** for the primary efficacy endpoint ‘percentage of patients who achieve and maintain reduction of sUA < 6 mg/dL for at least 80% of the time during Treatment Period 6 by Day 28’ is defined as follows:

- Population: Of all patients with gout refractory to conventional treatment defined by the study inclusion / exclusion criteria, the analysis population will include patients who were randomized to study treatment and who were dosed (ITT population)
- Variable: Binary variable indicating response status, whereby a responder is defined as a patient who has sUA < 6 mg/dL for at least 80% of the time during TP6.
- Population-level summary: Difference in the percentage of treatment responders of each SEL-212 treatment group versus placebo.
- Intercurrent events:
  - o Meeting the pre-defined treatment stopping criteria is considered as lack of efficacy and will be defined as treatment failures according to the composite strategy
  - o Premature stopping of study treatment due to treatment-related or non-treatment related AE, with the exception of a positive COVID-19 test result along with severe or critical symptoms of COVID-19, will be considered as treatment failure according to the composite strategy
  - o Premature stopping of study treatment due to a positive COVID-19 test result along with severe or critical symptoms of COVID-19 will be defined as treatment failures according to the composite strategy
  - o Death will be considered as treatment failure and will be treated according to the composite strategy
  - o Use of prohibited medication that lower sUA levels will be considered as treatment failure and will be treated according to the composite strategy
  - o All other intercurrent events (e.g. use of prohibited medication that do not lower sUA levels but are classified as a major protocol deviation) will be treated using the treatment policy strategy, i.e. the assessment of sUA in TP6 up to Day 28 will be used

The sample size estimation for the study is based on the main estimand for the primary efficacy endpoint from version 5.0 of the Protocol, but following an amendment to version 6.0, which additionally included patients presenting severe or critical symptoms of COVID-19 with a positive COVID-19 test result, and patients who missed all sUA assessment during TP6, as non-responders, it was determined that the same sample size is justified for the modified estimand.

A second estimand for the primary efficacy endpoint is defined using the same population, variable and population-level summary as in the main estimand, but with applying the treatment policy strategy in case of all intercurrent events (i.e. all month 6 assessments until Day 28 will be used even for patients who have discontinued the study drug) with exception of deaths, where the composite strategy will be used.

**This document is confidential.**

A third estimand for the primary efficacy endpoint is defined using the same population, variable and population-level summary as in the main estimand, but applying the composite strategy for all intercurrent events, i.e. all of the above listed events will be considered as treatment failures.

A fourth estimand for the primary efficacy endpoint is defined using the same population, variable and population-level summary as in the main estimand, but the intercurrent event handling of premature stopping of study treatment due to a positive COVID-19 test result along with severe critical symptoms of COVID-19 will be handled according to the treatment policy strategy.

The main, second and third estimands will be repeated three times, once with the population changed to the mITT, and the other with the population changed to the all randomized set, and thirdly with the population changed to the PP set.

## **6.2. Estimands for Key Secondary Efficacy**

### **6.2.1. Estimands for 'Reduction of mean sUA as computed by subtracting the Baseline sUA level from the mean sUA during Treatment Period 6'**

The main estimand for the key secondary efficacy endpoint 'Reduction of mean sUA as computed by subtracting the Baseline sUA level from the mean sUA during Treatment Period 6' is defined as follows:

- Population: Of all patients with gout refractory to conventional treatment defined by the study inclusion / exclusion criteria, the analysis population will include patients who were randomized to study treatment and who were dosed (ITT population)
- Variable: Continuous variable showing the difference between the mean sUA value recorded in TP6 and the baseline sUA value for each individual.
- Population-level summary: Difference in LS means between each SEL-212 treatment group vs. placebo.
- Intercurrent events:
  - o All intercurrent events (as listed in 6.1 for the primary estimand) except deaths will be considered using the treatment policy strategy
  - o For deaths, the last available value will be used (while-on-treatment strategy), i.e. the baseline sUA value will be subtracted from mean sUA values across the most recently attended TP.

A second estimand for this key secondary endpoint will be defined similarly to the main estimand but with using the while-on-treatment strategy for all intercurrent events (as listed in 6.1 for the primary estimand).

The main and second estimands will be repeated three times, once with the population changed to the mITT, and the other with the population changed to the all randomized set, and thirdly with the population changed to the PP set.

This document is confidential.

**6.2.2.** Estimands for 'Percent reduction of mean sUA as computed by subtracting the Baseline sUA level from the mean sUA during Treatment Period 6'

The main estimand for the key secondary efficacy endpoint 'Percent reduction of mean sUA as computed by subtracting the Baseline sUA level from the mean sUA (area under the sUA time curve) during Treatment Period 6' is defined as follows:

- Population: Of all patients with gout refractory to conventional treatment defined by the study inclusion / exclusion criteria, the analysis population will include patients who were randomized to study treatment and who were dosed (ITT population)
- Variable: Continuous variable showing the percentage difference between the mean sUA value recorded in TP6 and the baseline sUA value for each individual, i.e. the  $(\text{mean TP6 sUA value} - \text{baseline sUA value}) \div \text{baseline sUA value} \times 100$ .
- Population-level summary: Difference in LS means between each SEL-212 treatment group vs. placebo.
- Intercurrent events:
  - o All intercurrent events (as listed in 6.1 for the primary estimand) except deaths will be considered using the treatment policy strategy
  - o For deaths, the last available value will be used (while-on-treatment strategy), i.e. the baseline sUA value will be subtracted from mean sUA values across the most recently attended TP  $\div \text{baseline sUA value} \times 100$ .

A second estimand for this key secondary endpoint will be defined similarly to the main estimand but with using the while-on-treatment strategy for all intercurrent events (as listed in 6.1 for the primary estimand).

The main and second estimands will be repeated three times, once with the population changed to the mITT, and the other with the population changed to the all randomized set, and thirdly with the population changed to the PP set.

**6.2.3.** Estimands for 'The change from Baseline to Day 28 of Treatment Period 6 in the physical summary score of the Short Form Health Survey (SF-36)'

The main estimand for the key secondary efficacy endpoint 'Change from Baseline to Day 28 of TP6 of the Physical Summary Score of the Short Form Health Survey (SF-36)' is defined as follows:

- Population: Of all patients with gout refractory to conventional treatment defined by the study inclusion / exclusion criteria, the analysis population will include patients who were randomized to study treatment and who were dosed (ITT population)
- Variable: Continuous variable showing the change from Baseline to 6 months after start of study treatment (D28 of Treatment Period 6).
- Population-level summary: Difference in LS means between each SEL-212 treatment group versus placebo in the change from baseline in summary score of SF-36 questionnaire.
- Intercurrent events:

This document is confidential.

- All intercurrent events (as listed in 6.1 for the primary estimand) except deaths will be considered using the treatment policy strategy
- For deaths, the last available value will be used (while-on-treatment strategy)

A second estimand for this key secondary efficacy endpoint will be defined similarly to the main estimand but with using the while-on-treatment strategy for all intercurrent events (as listed in 6.1 for the primary estimand).

The main and second estimands will be repeated three times, once with the population changed to the mITT, and the other with the population changed to the all randomized set, and thirdly with the population changed to the PP set.

**6.2.4. Estimands for 'In patients with tophi at Baseline, the percentage of patients with at least PR (as best response) in overall tophus response evaluation until Day 28 of Treatment Period TP6'**

The main estimand for the key secondary efficacy endpoint 'percentage of patients with at least PR (as best response) in overall tophus response evaluation until D28 of TP6 in patients with tophi at baseline' is defined as follows:

- Population: Of all patients with gout refractory to conventional treatment defined by the study inclusion / exclusion criteria, the analysis population will include patients who were randomized to study treatment, who were dosed (ITT population) and had tophi at baseline.
- Variable: Binary variable indicating whether the patient had experienced at least a PR (as best response) or not in overall tophus response until Day 28 of TP6. This variable corresponds to the assessment of tophus reduction compared to baseline.
- Population-level summary: Difference in the percentage of patients with at least PR (as best response) in overall tophus response between each SEL-212 treatment group versus placebo.
- Intercurrent events:
  - All intercurrent events (as listed in 6.1 for the primary estimand) except deaths will be considered using the treatment policy strategy
  - For deaths, the last available tophus response assessment will be used (while-on-treatment strategy)

A second estimand for this key secondary endpoint will be defined similarly to the main estimand but with using the while-on-treatment strategy for all intercurrent events (as listed in 6.1 for the primary estimand).

The main and second estimands will be repeated three times, once with the population changed to the mITT, and the other with the population changed to the all randomized set, and thirdly with the population changed to the PP set, restricted each time to those who had tophi at baseline.

This document is confidential.

**6.2.5.** Estimands for 'Percentage of patients who achieve and maintain a reduction of sUA < 6 mg/dL for at least 80% of the time during Treatment Period TP6 in subset of patients with tophi at baseline'

The main estimand for the key secondary efficacy endpoint 'Percentage of patients who achieve and maintain a reduction of sUA < 6 mg/dL for at least 80% of the time during Treatment Period TP6 in subset of patients with tophi at baseline' is defined as follows:

- Population: Of all patients with gout refractory to conventional treatment defined by the study inclusion / exclusion criteria, the analysis population will include patients who were randomized to study treatment, who were dosed (ITT population) and had tophi at baseline.
- Variable: Binary variable indicating response status, whereby a responder is defined as a patient who has sUA < 6 mg/dL for at least 80% of the time during TP6.
- Population-level summary: Difference in the percentage of treatment responders of each SEL-212 treatment group versus placebo.
- Intercurrent events:
  - o All intercurrent events will be handled in the same way as the main estimand for the primary endpoint (as listed in [6.1](#) for the main estimand)

A second estimand for this key secondary endpoint will be defined similarly to the main estimand but with intercurrent events handled as per the second estimand for the primary endpoint (as listed in [6.1](#) for the primary estimand).

The main and second estimands will be repeated three times, once with the population changed to the mITT, and the other with the population changed to the all randomized set, and thirdly with the population changed to the PP set, restricted each time to those who had tophi at baseline.

**6.2.6.** Estimands for 'The change from Baseline to day 28 of Treatment Period 6 in number of Tender Joints'

The main estimand for the key secondary efficacy endpoint 'change from Baseline to D28 of TP6 in number of tender joints' is defined as follows:

- Population: Of all patients with gout refractory to conventional treatment defined by the study inclusion / exclusion criteria, the analysis population will include patients who were randomized to study treatment and who were dosed (ITT population)
- Variable: Continuous variable showing the absolute Change in number of tender joints from Baseline to 6 months after start of study treatment (D28 of Treatment Period 6).
- Population-level summary: Difference in LS mean change from baseline in number of tender joints between each SEL-212 treatment group versus placebo.
- Intercurrent events:
  - o All intercurrent events (as listed in [6.1](#) for the primary estimand) except deaths will be considered using the treatment policy strategy
  - o For deaths, the last available value will be used (while-on-treatment strategy)

*This document is confidential.*

A second estimand for this key secondary endpoint will be defined similarly to the main estimand but with using the while-on-treatment strategy for all intercurrent events (as listed in 6.1 for the primary estimand).

These analyses will be repeated for each background medication subgroup: i) no NSAIDs or colchicine, ii) NSAIDs no colchicine, and iii) colchicine.

The main and second estimands will be repeated three times, once with the population changed to the mITT, and the other with the population changed to the all randomized set, and thirdly with the population changed to the PP set.

